3.4.4 Vital Signs

Vital signs will be evaluated and assessed at screening, randomization and all further study visits according to the SoA, Tables 1 of the CSP. Vital signs include tympanic temperature (°C), systolic blood pressure (mmHg), diastolic blood pressure (mmHg), pulse rate (beats per minute), respiratory rate (breaths per minute), height (cm, baseline only) and weight (kg). Absolute change from baseline will be calculated for each post-dose visit.

3.4.5 Electrocardiograms

Electrocardiogram (ECG) assessments will be performed at screening, randomization, EOT, and follow-up (as specified in the SoA), and according to clinical judgement in connection with severe hypokalaemia (sK+ <3.0 mmol/L), severe hyperkalemia (sK+>6.0 mmol/L) or any symptoms or clinical events suggesting cardiac arrhythmia. ECG parameters will include mean, minimum and maximum heart rate (beats/min), aggregate PR interval (msec), P wave duration (msec), QRS duration (msec), QT interval (msec), QTcB interval (msec), QT interval corrected by the Fridericia method (QTcF) interval (msec) and RR interval (msec). The absolute change from baseline will be calculated for each post-dose visit.

3.4.6 Physical Exam

A complete physical examination is performed at screening, randomization and all further study visits according to the SoA, Tables 1 of the CSP. Physical examination will include an assessment of general appearance, respiratory, cardiovascular, abdomen skin, head and neck (including ears, eyes, nose and throat), lymph nodes, thyroid, musculoskeletal (including spine and extremities) and neurological systems. Body weight and height are measured at the screening visit and weight will then be measured at randomization and all further study visits according to the SoA.

4 ANALYSIS METHODS

The principal analyses outlined in this statistical analysis plan will be conducted by Covance Inc., in accordance with the contract with AstraZeneca Pharmaceuticals LP and following the Excellence in Medical Partnership for Outsourced Worldwide Evidence Research (EMPOWER) description of services.

The below mentioned general principles will be followed for analyses:

Descriptive statistics will be used for all variables, as appropriate. Continuous variables will be summarised by the number of observations, mean, standard deviation, median, Q1, Q3, minimum and maximum. Categorical variables will be summarized by frequency counts and percentages for each category.

Unless otherwise stated, percentages will be calculated out of the analysis set total for the treatment group.

For continuous data, the mean and median will be rounded to 1 additional decimal place compared to the original data. The standard deviation will be rounded to 2 additional decimal places compared to the original data. Minimum and maximum will be displayed with the same accuracy as the original data.

For categorical data, percentages will be rounded to 1 decimal place.

SAS® version 9.3 or higher will be used for all analyses

It is acceptable to present large numerical values in more appropriate units. For example, an AUC value of 123,000 ng h/mL may be reported as 123 μ g h/mL instead. It is however, important to keep the units consistent within the report and the precision consistent with that prior to conversion.

In general, for all endpoints the last observation before the first dose of study treatment in the open-label period will be considered the baseline measurement, unless otherwise specified. For assessments on the day of first dose, where time is not captured, a nominal pre-dose indicator, if available, will serve as sufficient evidence that the assessment occurred prior to first dose.

Assessments on the day of the first dose when neither time nor a nominal pre-dose indicator are captured will be considered prior to the first dose if such procedures are required by the protocol to be conducted before first dose.

In all quantitative summaries from baseline, variables will be calculated as the post-treatment value minus the value at baseline. The percentage change from baseline will be calculated as (post-baseline value – baseline value) / baseline value x 100. Absolute and percentage change will be summarized.

Safety and treatment exposure data will be summarised based upon the SSO and SSR analysis sets separately. Analyses using the SSO analysis set will be restricted to visits 1 and 2 (if applicable). Study population and demography data will also be summarized using the SSO and SSR analysis sets.

4.1.1 Handling of missing dates

Incomplete dates (partial or missing dates where a full date is permissible) will be presented in the data listings as recorded on the eCRF. However, for use in calculations (for instance in calculation of the duration of an AE or medication use), dates will be estimated as follows:

4.1.1.1 Partial start dates

If the year is unknown, then:

• The date will not be imputed, and will be assigned a missing value

If the month is unknown, then:

- If the year matches the year of the first dose date in the open-label period, then impute the month and day of the first dose date.
- Otherwise, assign the month as January

If the day is unknown, then:

- If the month and year match the month and year of the first dose date in the open-label period, then impute the day of the first dose date.
- Otherwise, assign the day as 1st of the month.

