3.4.2 Adverse Events

Adverse events (AEs) and Serious adverse events (SAEs) will be collected from start of the open-label correction phase, throughout the treatment period and including during the follow-up period. In addition, SAEs will be recorded from the time of signing the informed consent form and will continue throughout the clinical study until the end of any follow-up prior; this applies even if the subject has not received any study treatment (as per the SOP: Reporting of Individual Safety Events in Clinical Studies). SAEs which occur after the end of the clinical study but with a suspected causal relationship to the IP will be reported by the investigator but will not be included in summary tables and listings.

A treatment emergent AE (TEAE) will be defined as an AE with the start date on or after the first dose date and up to (and including) 7 days after the last dose date or an AE which starts prior to first dose of IP (i.e. before study day 1) which subsequently worsen in severity on or after the date of first dose of IP and up to and including 7 days following the date of last dose of study medication. AEs which occur more than 7 days after the last dose date will only be listed. Similarly, the number of patients experiencing SAEs, AEs that led to withdrawal, AEs that led to death and treatment related AEs, and number of such events, will be summarized by treatment group.

AEs will be further categorized as either occurring during the open-label period, if the start date is on or after the first dose date during the open-label correction period and prior to the date of the first dose of treatment during the randomized placebo-controlled period, or occurring during the randomized placebo-controlled period if the start date is on or after the date of the first dose of treatment during the randomized placebo-controlled period.

The Medical Dictionary for Regulatory Activities (MedDRA) (using the latest or current MedDRA version) will be used to classify AEs system organ class (SOC) and preferred term (PT).

If the relationship to treatment is missing, then the AE will be considered as possibly related to treatment.

Other significant adverse events

An overview of edema-related events (grouped terms include preferred terms of edema, edema peripheral, generalized edema, fluid overload, fluid retention, hypervolemia, localized edema, and peripheral swelling)and instances of sK+ <3.5 will be presented.

Deaths

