4.2.5 Previous and Concomitant Medications

Medications received prior to or concomitantly with study treatment will be coded using the WHO Drug Dictionary [Version March 2020 (or a later version if updated during the study)], Anatomical Therapeutic Chemical (ATC) Classification codes.

Prior medications and concomitant medications are as defined as follows:

Prior medications are those taken with a stop date prior to the first dose date of study treatment during the open-label correction period.

Concomitant medications during the open-label correction period are those with a start date anytime before the first dose date of study treatment during the randomized placebocontrolled period and a stop date on or after the first dose of study treatment during the openlabel correction period. Concomitant medications during the randomized placebo-controlled period are those with a stop date on or after the first dose date of study treatment during the randomized placebo-controlled period.

If a medication cannot be classified as "prior" or "concomitant during the open-label correction period" or "concomitant during the randomized placebo-controlled period" after applying imputation rules for missing/incomplete dates, it will be classified as concomitant during the randomized placebo-controlled period.

Concomitant medications during the open-label correction and randomized placebo-controlled periods will be further categorized by those allowed and disallowed. Disallowed concomitant medications are defined in the CSP Section 6.8 as starting on RAASi therapy during the trial (ATC level 2 code C09) or sodium-glucose transport protein 2 inhibitor therapy. Furthermore, several medications which are described as restricted will also be included as disallowed concomitant medications.

Prior medications, allowed/disallowed concomitant medications during the open-label correction period and allowed/disallowed concomitant medications during the randomized placebo-controlled period will be listed together. Allowed/disallowed concomitant medications during the open-label correction period will be summarized using the SSO and presented in total. Allowed/disallowed concomitant medications during the randomized placebo-controlled period will be summarized separately by treatment group and overall using the SSR.

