4.2.8 Safety

4.2.8.1 Adverse Events

An overall summary table of the number of subjects experiencing each category of AEs will be produced using the SSO and SSR. Analyses using the SSO will be restricted to AEs which occurred during the open-label correction period and will be presented overall. Analyses using the SSR will include AEs which occurred during the randomized placebo-controlled period and will be presented by treatment group received during the randomized placebo-controlled period and overall.

Any AE occurring within the defined 7-day follow-up period after discontinuation of IP will be included in the AE summaries. Treatment emergent adverse events (TEAEs) occurring prior to first dose of IP (i.e. before study day 1) which subsequently worsen in severity following dosing will be presented in the summary tables.

An overview table will summarize the number and percentage of subjects with at least one of the following AEs, where patients with more than one AE in a particular category are counted only once in that category, as well as the absolute counts of number of AEs. For the overall summary of subjects with any AEs, in the safety set randomized analysis group, the event rate will be displayed. This will be calculated as the Number of subjects with AEs divided by the total number of days at risk for AEs across all subjects in given group, multiplied by 365.25 multiplied by 100.

- Any AEs
- · Any AEs assessed by investigator as possibly related to treatment
- Any AEs with outcome of death
- Any SAEs (including events with outcome of death)
- Any SAEs leading to treatment discontinuation
- Any AEs leading to treatment discontinuation
- Any AEs leading to dose reduction of study treatment
- Any AEs leading to dose interruption of study treatment

• Any AEs leading to study discontinuation

The number and percentage of subjects reporting each AE will be summarized by system organ class (SOC) and preferred term (PT). Tables will be sorted by international order for SOC and PTs will be sorted alphabetically. The following summaries will be produced using the SSO and SSR:

- AEs by SOC and PT;
- Most common AEs (>5% in any treatment group) by SOC and PT;
- AEs assessed by investigator as possibly related to treatment, by SOC and PT;
- AEs by relationship to treatment, by SOC and PT;
- AEs by maximum intensity, by SOC and PT;
- AEs assessed by investigator as possibly related to treatment, by maximum intensity, SOC and PT;

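### Adverse events with an unknown start day in the first-dose month are dated to the first open-label dose and so leave the by-arm safety tables, although most will have begun in the randomised period

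*SAP*

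**What the plan says.** **Imputation.** SAP section 4.1.1 introduces its rules broadly: "for use in calculations (for instance in calculation of the duration of an AE or medication use), dates will be estimated as follows". Section 4.1.1.1 then covers start dates. When only the day is unknown: "If the month and year match the month and year of the first dose date in the open-label period, then impute the day" of that dose. When the month is unknown: "If the year matches the year of the first dose date in the open-label period, then impute the month and day of the first dose" (the sentence ends with the word date). If nothing matches, the first of the month, or January, is used.

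**Assignment to a period.** Section 3.4.2 uses the start date alone. An AE is open-label "if the start date is on or after the first dose date during the open-label correction period" and before the first randomised dose. It belongs to the randomised period "if the start date is on or after the date of the first dose of treatment during the randomized placebo-controlled period".

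**Tables.** Section 4.2.8.1 follows that split: "Analyses using the SSR will include AEs which occurred during the randomized placebo-controlled period", shown by treatment received. Open-label AEs go to the Safety Set Open tables, which section 2.1 analyses as a single group.

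**Length of the periods.** Section 1.2 gives an open-label phase of up to 48 hours, then four weeks of randomised treatment and a 7-day follow-up.

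**The concern.** Anchoring a doubtful start date to the first dose is a common way to keep the event treatment-emergent, and it works in a trial with one treatment period. This trial has two, and the between-arm safety comparison uses only the second. The anchor is the first dose of the first period, which always precedes the first randomised dose. Every AE that meets the matching rule is therefore placed in a phase of one or two days, even when a recorded end date late in the randomised period makes a later onset more plausible. Section 4.1.1.2 tests imputed end dates for illogical results, but no such test exists for start dates.

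At stake are the by-arm AE counts. An AE that began on randomised SZC or on placebo would be missing from its arm and be counted under open-label SZC. The trial ended early with a small sample (amendment history and section 6), so even one moved event could show in a percentage.

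**Working it through.** The SAP gives no figure to reproduce. The check has two parts.

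**1. Does the text force the misfiling?** Section 4.1.1.1 sets the start to the first open-label dose date. Section 3.4.2 calls any start from that date up to the day before the first randomised dose open-label. Table 1 puts randomisation on Day 2 or 3, so the imputed Day 1 is always on the open-label side. Section 4.2.8.1 then excludes the AE from the by-arm tables. No other section overrides this for AEs.

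**2. What share of such AEs began in the randomised period?** Assumptions, none of them given in the SAP:
- the first dose is equally likely on each day d of a month of M days;
- there are L = 1 or 2 open-label days before the first randomised dose;
- AEs start at a constant daily rate up to Day 36.

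On-study days left in the first-dose month are M − d + 1. Those on or after the first randomised dose are max(0, M − d + 1 − L). Summing each over d = 1 to M:

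| M | On-study days | Randomised, L = 1 | Randomised, L = 2 |
|---|---|---|---|
| 28 | 406 | 378 (93.1%) | 351 (86.5%) |
| 30 | 465 | 435 (93.5%) | 406 (87.3%) |
| 31 | 496 | 465 (93.8%) | 435 (87.7%) |

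In a 30-day month the randomised share exceeds one half for 28 of the 30 possible first-dose dates (L = 1) or 26 of 30 (L = 2). It fails only when the first dose falls in the last few days of the month.

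**More AEs during open-label dosing.** Let the open-label daily rate be k times the randomised rate. In a 30-day month the open-label days sum to 465 − 435 = 30 (L = 1) or 465 − 406 = 59 (L = 2). The share is 435/(435 + 30k) or 406/(406 + 59k):

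| k | L = 1 | L = 2 |
|---|---|---|
| 3 | 435/525 = 82.9% | 406/583 = 69.6% |
| 5 | 435/585 = 74.4% | 406/701 = 57.9% |
| 7 | 435/645 = 67.4% | 406/819 = 49.6% |

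**Month unknown, year matching.** With the first dose uniform over 365 days, on-study days within the year sum to 330 × 36 + 630 = 12,510. The randomised share is (12,510 − 365)/12,510 = 97.1% for L = 1 and (12,510 − 729)/12,510 = 94.2% for L = 2.

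**Reach of the day-unknown rule.** For M = 30, the part of the randomised period (to Day 36) that lies in the first-dose month is 435/(30 × 35) = 41.4% for L = 1 and 406/(30 × 34) = 39.8% for L = 2.

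**The case against.** **Scope.** Section 4.1.1 names AE duration, not period assignment, as its example, and section 3.4.2 does not refer to the imputation rules. Applying them there is a reading. It is the likeliest one, because the example is introduced as an instance only and no other start-date rule exists.

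**Few events.** AEs are collected prospectively from the start of the open-label phase, with visits on Days 1, 2, 2 or 3, 8, 15, 22, 29 and 36. Missing start days should be rare and missing months rarer. Only about 40% of randomised-period days lie in the first-dose month. This stands. The 87% to 94% is a share of the AEs caught by the rule, not an effect on any table.

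**Uniform onset.** The open-label phase uses 10 g three times daily, so early AEs may be more frequent. The sensitivity analysis answers most of this: the randomised period keeps the majority until the open-label rate is about seven times higher with two open-label days.

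**Nothing is hidden.** Section 4.1.1 keeps dates in listings as recorded. Section 4.2.8.1 lists every AE with its timing and the treatment at the time of the event. The AE stays treatment-emergent and is counted in the open-label tables. The AE summaries carry no formal test. All of this stands and keeps the point minor.

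**Two stronger inferences fail.** A reader might infer that the rule tilts the comparison towards SZC. The documents do not support that: one rule applies to both arms of a double-blind trial, and AEs that began on randomised SZC are moved just as those on placebo are. A reader might also see a contradiction with section 4.2.5, where a medication that cannot be classified is handled thus: "it will be classified as concomitant during the randomized placebo-controlled period". That default applies only after the same date imputation has been tried, and concomitant status in the randomised period depends on the stop date. It is not an opposite rule.

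**Conclusion.** The point holds as a minor weakness in the safety analysis. Read together, sections 4.1.1.1, 3.4.2 and 4.2.8.1 place every AE with a matching partial start date in the open-label phase and keep it out of the by-arm tables. Most such AEs will have begun in the randomised period: about 87% to 94% in a 30-day month under uniform onset, and about 58% to 74% if the open-label daily rate is five times higher. These shares rest on assumed distributions of first-dose day and onset.

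The shift is between periods. It understates randomised-period AEs and loses information, but no bias between arms is shown. The SAP does not say how many AEs will have partial start dates; the number is probably small.

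**What to change.** Add one AE-specific rule to section 4.1.1.1. For patients dosed in the randomised period, if the known part of the AE start date matches the first randomised dose date, impute that date, unless the AE end date or other recorded information shows an earlier onset. Otherwise keep the present rule. Section 3.4.2 should state that imputed dates are used to assign AEs to periods.

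The AE stays treatment-emergent, because the randomised dose follows the first dose. The rule also covers a first dose at the end of a month with the first randomised dose on the 2nd of the next, where imputing the 1st would again give open-label.

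The cost is one sentence and a small programming change. The downside is that a few true open-label AEs will be counted in the randomised period. Under uniform onset that is at most 30/465 = 6.5% (one open-label day) or 59/465 = 12.7% (two) of the day-unknown AEs in a 30-day first-dose month, and about 6% to 14% over months of 28 to 31 days. The present rule misfiles about 86% to 94%.

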4.1.1.2 Partial end dates

If the year is unknown, then the date will not be imputed and will be assigned a missing value.

If the month is unknown, then assign December.

If the day is unknown, then assign the last day of the month.

If the above rules for end dates result in an illogical date with regard to the dates the subject was in the study, then the end date will be replaced with the subject's date of completion/discontinuation.

4.2 Analysis methods

4.2.1 Subject Disposition and Analysis Sets Analyzed

Subject disposition will be listed and summarized by treatment group and overall. The number and percentage of subjects in the following categories will be summarized for subjects in the screened set:

- Screened;
- Did not enter open-label period (Screening failures) and associated reasons;
- Entered the open-label period and received treatment
- Entered the open-label period and did not receive treatment and associated reasons
- Randomized;
- Not randomized (Open-label period failure) and associated reasons;
- Randomized and received treatment;
- Randomized, did not receive treatment and associated reasons;
- Completed the study;
- Discontinued treatment and associated reasons (including use of rescue treatment);
- Terminated study and associated reasons;

The denominator used for percentages will be calculated as follows. The denominator for subjects who are screened or who did not enter the open-label period (and associated reasons) will be calculated using the number of screened subjects. The denominator for subjects who entered the open-label period and received treatment, who entered the open-label period and did not receive treatment (and associated reasons), randomized and not randomized (and associated reasons) will be calculated using the number of subjects who entered the open-label period. The remaining subject disposition categories will use the number of subjects who were randomized for the denominator. Categories will still be presented if 0 subjects satisfy the criteria.

The number of subjects in each of the analysis sets and the reasons for exclusion from each will be summarized for all screened subjects by treatment group and overall.

4.2.2 **Protocol Deviations**

All important protocol deviations (Section 2.2) leading to exclusion from the PPS will be listed and summarized by treatment group and overall for the FAS. Important protocol deviations will be further classified as either pandemic-related or excluding pandemic related important protocol deviations and will be summarized by treatment group and overall for the FAS.

4.2.3 Demographics and Other Baseline Characteristics

Demographic and baseline characteristics will be listed and summarized in total for the SSO and by treatment group and total for the SSR and FAS. The demographic and baseline characteristics include the following:

- Age (years);
- Age groups (>18 to ≤65, >65 to ≤85 and >85 years);
- Sex (male, female);
- Race category (White, Black or African American, Asian, Native Hawaiian or Other Pacific Islander, American Indian or Alaskan Native, Other);
- Ethnicity (Hispanic or Latino, Not Hispanic or Latino);
- CKD status at baseline (3, 4 or 5);
- Chronic Heart Failure at baseline (No, Yes) [Determined as medical history with MedDRA coded preferred term of cardiac failure chronic]
- Diabetes status at baseline (No, Yes);

No formal tests of statistical significance will be performed on the demographic and baseline data.

A separate table will summarize the subject characteristics at baseline and will be listed and summarized in total for the SSO and by treatment group and total for the SSR and FAS. They will include:

- Baseline height (cm);
- Baseline weight (kg);
- Baseline body mass index (kg/m²) [calculated as (baseline weight/baseline height² where weight is in kg and height is in m];

Other baseline measurements, such as vital signs and ECG results, will be reported with postbaseline measurements.

